## PROTOCOL SUMMARY

[figure not shown]
Title	STILL 3 Study
Brief Summary	
The purpose is to provide further evidence concerning the efficacy of tACS for treatment of auditory hallucinations and to evaluate an exploratory maintenance stimulation paradigm to prolong the duration of stimulation-induced clinical benefits. We will study 40 eligible males and females diagnosed with schizophrenia or schizo-affective disorder. The longitudinal experimental design is a two-treatment, 4-sequence, multi-period randomized crossover design. During the first week, the enrolled participants will have 5, daily, 40-minute stimulation sessions. At the end of the first week, the participants will begin an 8-week maintenance regimen of weekly 40-minute stimulation sessions.
 
A randomization protocol will be used to assign each participant to either a sham regimen or an active regimen during the first week, and to a sham or active maintenance regimen. Equal numbers of participants will be assigned by random allocation to the four treatment-sequence groups: tACS-tACS, tACS-sham, sham-tACS, sham-sham.
 
Participation will involve 1 to 18 visits. At the initial phone session, informed consent will be obtained and subjects will be screened for eligibility. Participants will be contacted again in 2 weeks for a second phone screening session to determine stability of auditory hallucination symptoms, utilizing the Auditory Hallucinations Rating Scale (AHRS, attachment 3). If the AHRS scores are within <math>\pm 20\%</math> of their previous score, they will be considered eligible. If the AHRS scores do not fall within this range, participants will be rescheduled for a third or fourth screening session separated by 2 weeks. If, after the fourth screening session the participant does not have stable AHRS scores, they will not be eligible to participate.
 
Eligible participants will be scheduled for their daily stimulation sessions which will include a daily assessment of stimulation side-effects. Clinical assessments of auditory hallucinations will be administered with the AHRS and the self-administered Hamilton Program for Schizophrenia Voices (HPSVQ). These measurements will be assessed at the time of enrollment into the study (baseline), at the first day of stimulation, at the fifth day of stimulation, and once weekly for 8 weeks of maintenance stimulation sessions. Neurophysiological (EEG) and cognitive assays will be performed day 1 of stimulation, day 5 of stimulation, and at maintenance stimulation sessions for weeks 1, 3 and 8. In conjunction with

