Target Population	We will recruit 40 males and non-pregnant females ages 18-70 with a diagnosis of schizophrenia or schizoaffective disorder, who have at least 3 auditory hallucinations per week, with no change in medication dosing for at least 4 weeks, not currently taking any benzodiazepine medication, and have been clinically stable for at least 12 weeks, with no change in their level of care during that period. Participants will be recruited from the Chapel Hill, Durham and Raleigh areas.
Phase	Preliminary Study
Number of Sites	This is a single site study performed at University of North Carolina - Chapel Hill.
Study Agent	We will be using an active sham and 10 Hz tACS. Active sham treatment will include 10 seconds of ramp in to 20 seconds of 10 Hz tACS with a ramp out of 10 seconds for a total of 40 seconds of stimulation. The choice of an active sham is motivated to enhance success of patient blinding by mimicking skin sensations associated with tACS. 10 Hz tACS will also have a 10 second ramp in and ramp out with 40-minutes of stimulation for a total of 1220 seconds during the week of stimulation. During the maintenance week sessions, stimulation sessions will be a one session for a total of 40-minutes. Stimulation waveforms are sine-waves with a peak-to-peak amplitude of 2 mA.

Study Duration	This study will take 30 months to complete
Participant Duration	Eligible participants who complete this clinical trial will have a total of 15 to 18 visits; an initial session, 1 to 3 follow up screening sessions, 5 consecutive days of daily stimulation, 1 MRI scan session, and 8 once weekly maintenance stimulation sessions. Maintenance sessions will begin the week after the 5 days of stimulation have been completed. The initial screening session will take approximately 2 hours, each follow up screening session will last approximately 30 minutes, and the first day of stimulation will take approximately 4 hours. Days 2 through 4 of stimulation will take 1.5 hours each day. Day 5 of stimulation will last about 4 hours. The sMRI visit will last no longer than 2 hours. Maintenance stimulation sessions weeks 1 and 3 will take approximately 3 hours. Maintenance sessions weeks 2, 4, 5, 6, and 7 will take approximately 2 hours. Maintenance session week 8 will take approximately 5 hours. We estimate that total participation to be approximately 35-39 hours.

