Sham treatment will include 10 seconds of ramp in to 20 seconds of 10 Hz tACS with a ramp out of 10 seconds for a total of 40 seconds of stimulation. The rationale for this choice of an active sham is that it may enhance success of patient blinding by mimicking skin sensations associated with tACS. 10 Hz tACS will have a 10 second ramp in and ramp out with 40-minutes of stimulation for a total of 1220 seconds of stimulation, daily for five days. Stimulation waveform is a sine-wave with a peak-to-peak amplitude of 2 mA. In each treatment regimen, participants will stay in a relaxed and controlled state by watching a nature movie such as "ReefScape" during stimulation. The maintenance regimen will provide one 40-minute stimulation per week.

Eligible participants who complete this clinical trial will have a total of 15 to 18 visits; an initial screening session, a 2nd screening session, (if needed) 2 more follow up screening sessions, 5 days of daily stimulation sessions, 1 sMRI visit, and 8 weekly maintenance stimulation sessions. The initial phone screening session will take approximately 2 hours, and each follow up screening session will take approximately 30 minutes each. The first day of stimulation will take approximately 4 hours and days 2 through 4 of stimulation will take 1.5 hours each. The last day of stimulation will take about 4 hours. sMRI visits will last approximately 2 hours. Maintenance stimulation sessions weeks 1 and 3 will be approximately 3 hours each, maintenance weeks 2, 4, 5, 6, and 7 will be approximately 2 hours each, and the final maintenance stimulation session week 8 will be approximately 5 hours. We estimate that total participant participation duration will be approximately 35 to 39 hours. A small subset of participants will be recruited for a 12 week observational case study to assess the feasibility of long-term at-home maintenance treatment.

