## 6 STUDY INVESTIGATIONAL PRODUCT

### 6.1 STUDY PRODUCT DESCRIPTION

#### 6.1.1 DEVICE DESCRIPTION

Participants will be stimulated with the commercial, CE-certified Neuroconn Plus stimulator. The use of this device in this study has previously received a NSR designation on initial review by the full UNC IRB. The NeuroConn device description is as follows:

The DC-STIMULATOR is a CE-certified medical device for conducting non-invasive transcranial direct-current stimulation (TDCS) in humans. DC stimulation is used in clinical practice and in the research of stroke, epilepsy, migraine, tinnitus, depression, multiple sclerosis, dementia and chronic headache. The DC-STIMULATOR is a micro-processor-controlled constant current source. It meets the highest safety standards thanks to (hardware- and software-based) multistage monitoring of the current path. By continuously monitoring electrode impedance it can detect insufficient contact with the skin and automatically terminate stimulation, maximizing patient safety.

The device's alphanumeric display and the 4 touch keys allow various stimulation modes to be selected and stimulation parameters such as current strength, duration, fade-in and fade-out to be set.

DC-STIMULATOR features:

- 1 channel (anodal and cathodal stimulation possible)
- Adjustable current up to 5,000  $\mu$ A \*
- Adjustable application time up to 30 minutes \*
- 2 standard modes - single (continuous stimulation) and - pulse (cyclical stimulation activation/deactivation) with fade in and fade out
- Customer-specific programs possible (optional)
- "Study mode" for blind processing of genuine and 'pseudo' stimulation (optional)
- External trigger input (optional)

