#### **Day 5 of Stimulation (Visit 9)**

The participant will be asked to decide if they would like to complete the clinical assessments over the phone or in person. If they prefer the phone/webex, the participant will be contacted before coming into the lab and the AHRS (*Attachment 3*) and PANSS (*Attachment 5*) will be administered. Upon participant arrival at the lab, vital signs will be taken and documented at the beginning of the first stimulation session of the day. An EEG will then be administered, with ECG data also being collected at this time. The EEG recording will include resting state data along with an auditory task, and the EEG Questionnaire will be administered. The participant will receive 40-minutes of sham or 10 Hz tACS (as per the initial randomization) while sitting quietly with their eyes open. The *Reefscape* video will be played during the stimulation session. Each stimulation session will be followed by the stimulation adverse effects questionnaire. The BACS (*Attachment 6*) data collection assessments will be administered at the end of this session. If the participant opted to complete the clinical assessments in person, the AHRS (*Attachment 3*) and the PANSS (*Attachment 5*) will be administered at the end of this session. After the assessments are completed, the participant will then be paid at the completion of the session, and the first maintenance session will be scheduled for the second week after their last day of stimulation (one gap week in between).

---

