### 8 ASSESSMENT OF SAFETY

#### 8.1 SPECIFICATION OF SAFETY PARAMETERS

There will be three different assessments used to ensure participant safety. First, vitals will be recorded at the beginning of each session. This assessment is used to monitor any physiological changes.

A Positive and Negative Syndrome Scale will be administered before the first stimulation session and on the last day of stimulation as well as at the one month follow up. This tool is used to assess any changes in symptoms associated with this disorder. We do not expect any changes in these symptoms; additionally we did not find any changes in related clinical trials (IRB# 13-2995, IRB #14-3285). Should there be a significant change in PANSS rating scores, (>25% increase) we will direct the participant to [name] for further follow up and file a AE report.

The Columbia Suicide Severity Rating Scale will be administered at the initial session and roughly monthly intervals thereafter. The tool is used to assess recent and lifetime suicidality and will primarily determine if [name] should be called to conduct an acute assessment. Should a participant answer “yes” to items 3,4, or 5 on the Suicidal Ideation section or “yes” to any Suicidal Behavior question within a recent time period (specified above), [name] will be called to conduct an acute assessment and we will file an AE report.

After each stimulation session, a stimulation adverse effects questionnaire (*Attachment 1* and *Attachment 2*) will be administered. This tool is used to document any side effects experienced during stimulation. The researcher will also check with the participant throughout the 20 minute stimulation sessions to make certain no discomfort is felt. The stimulation session will be terminated if the participant reports having unmanageable discomfort or pain (more than “moderate”). Additionally, this information will be reported on an AE report form (*Appendix A*) and an AE log (*Appendix B*).

---

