Participation in this study includes 1 to 18 sessions, with one session being an initial screening session, three possible follow-up screening sessions, then five, twice daily stimulation sessions, followed by a session for an MRI scan and 8 weeks of once weekly stimulation sessions. The five days of stimulation sessions need to be on consecutive days preferably Monday through Friday, with the second session occurring 3 hours after the completion of the first session. The maximum compensation for this study is \$760 for completing all of the sessions. Are you still interested in participating?

(If 'No', thank them for their time)

(If 'Yes', proceed)

Great! In order to make sure you're eligible for the study, I need to ask you a few questions. Please answer yes or no. You do not need to provide any further details.

(If the answer given is not the same as the answer shown, thank the individual for his or her interest and say unfortunately, they do not qualify for the current study)

- Are you 18 years old or older? (Yes)
- Have you ever, or are you currently being treated for a neurological condition (i.e. epilepsy)? (No)
- Are you currently taking any benzodiazepines? (No)
  - What medications are you currently prescribed?
- Do you use any drugs or medications not prescribed, including marijuana, cocaine, etc.? (No)
  - Please note that we will conduct a urine drug test at the initial screening session.
- Have you ever had brain surgery? (No)
- Do you have any brain devices or implants, including a cochlear implant or aneurysm clip? (No)
- Have you ever been diagnosed with a traumatic brain injury? (No)
- (For females only), Is there a chance you may be pregnant? (No)
- Have you ever been diagnosed with a mental or psychiatric illness by a professional (i.e. a psychiatrist or other licensed clinician)? (Yes)
  - If yes: What were you diagnosed with?
- Do you ever experience auditory hallucinations (i.e. hearing voices or noises no one else can hear)? (Yes)
  - If yes: On average how often does this happen per week?

Follow-up questions:

- Do you wear glasses/contact lenses?
  - Could you bring your contact lenses for the study visits instead of wearing your glasses?

(If answered according to all indicated responses, continue)

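### The active session is defined as 40 minutes but totalled as 1220 seconds, which is 20 minutes plus ramps, and other wording on session length and sessions per day does not match the visit procedures

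*Combined protocol and SAP*

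**What the plan says.** **Regimen definition.**
- Section 4.2: "40-minutes of stimulation for a total of 1220 seconds of stimulation, daily for five days", with 10 seconds of ramp in and 10 of ramp out.
- Protocol Summary, Study Agent row: "40-minutes of stimulation for a total of 1220 seconds during the week of stimulation". The next sentence of that row gives each maintenance session as 40 minutes.

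**Schedule and visit procedures.**
- Protocol Summary, Brief Summary row: "the enrolled participants will have 5, daily, 40-minute stimulation sessions", followed by weekly 40-minute maintenance sessions.
- Sections 7.4.3, 7.4.5 and 7.4.6 describe one 40-minute stimulation at each stimulation visit, in the first week and in maintenance.
- Visit lengths (Protocol Summary and section 4.2): about 4 hours on days 1 and 5, and 1.5 hours on each of days 2 to 4.

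**Wording that does not match.**
- Section 8.1: staff check on the participant "throughout the 20 minute stimulation sessions to make certain no discomfort is felt".
- Section 7.4.3, Day 5: vital signs are taken "at the beginning of the first stimulation session of the day", although the same paragraph describes a single 40-minute stimulation.
- Telephone recruitment script: five days of twice-daily stimulation, "with the second session occurring 3 hours after the completion of the first session", and a 7-hour session that includes a 3-hour break.
- Section 6.1.1, device features: "Adjustable application time up to 30 minutes", marked with an asterisk whose footnote is not visible.

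**The concern.** The duration and the total stand in the same sentence of the intervention's definition, and they cannot both be true. Someone setting up the stimulator from that sentence could arrive at either of two session lengths, one about twice the other. The unmatched wording elsewhere makes it harder to dismiss the total as a lone typing slip.

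Three things depend on the answer.
- The active-regimen mean in the primary model (section 10.2) is the mean under whatever exposure was delivered. A report written from this document could not state that exposure unambiguously.
- Section 10.2 attributes the expected difference between the periods under active treatment to weekly rather than daily stimulation, and the difference between the two period parameters is half of the primary null hypothesis. The Study Agent row attaches 1220 seconds to the first week and 40 minutes to maintenance. Read literally, session length would change between periods along with frequency.
- Section 7.4.1 says the approved telephone script is used for all telephone screenings, so candidates hear a schedule that the visit procedures do not contain.

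**Working it through.** **Inputs.** Ramps of 10 s + 10 s, 40 minutes, the 1220 s total and the sham components come from section 4.2; the 20-minute wording from section 8.1; two sessions a day, the 3-hour gap and the 7-hour session from the telephone script; visit lengths from the Protocol Summary and section 4.2.

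**Formula.** Seconds per session = minutes × 60 + ramp in + ramp out.

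**Step 1: the plan's own sums.**
- Sham: 10 + 20 + 10 = 40 s. This agrees with the stated sham total, so the plan counts ramps in its totals.
- Active at 40 minutes: 40 × 60 + 10 + 10 = 2420 s. The stated 1220 s is not reproduced. With the ramps inside the 40 minutes the figure is 2400 s, still not 1220.
- Active at 20 minutes: 20 × 60 + 10 + 10 = 1220 s. This is the stated figure exactly.
- Ratio per session: 2420 / 1220 = 1.98.

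**Step 2: 1220 s as a weekly total.** The Study Agent row can be read this way. Five sessions of 2420 s make 12,100 s, and 12,100 / 1220 = 9.9. That reading would leave 1220 / 5 = 244 s per day, which matches no other statement.

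**Step 3: exposure over the first week.** The script gives no session length, so both are shown.

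| Reading | Seconds per day | Seconds over 5 days |
|---|---|---|
| Once daily, 1220 s | 1220 | 6,100 |
| Once daily, 40 min + ramps | 2420 | 12,100 |
| Twice daily, 1220 s | 2440 | 12,200 |
| Twice daily, 40 min + ramps | 4840 | 24,200 |

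The two once-daily readings differ 1.98-fold. Twice daily at 1220 s is almost the same as once daily at 40 minutes (12,200 / 12,100 = 1.01).

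**Step 4: twice-daily sessions against the visit lengths.**
- Days 2 to 4: 1.5 hours per visit against a gap of 3 hours between sessions. Two sessions do not fit.
- Days 1 and 5: about 4 hours per visit against the script's 7 hours.
- Whole study: 2 (initial) + 0.5 to 1.5 (follow-up screening) + 4 (day 1) + 3 × 1.5 (days 2 to 4) + 4 (day 5) + 2 (MRI) + 2 × 3 (maintenance weeks 1 and 3) + 5 × 2 (weeks 2 and 4 to 7) + 5 (week 8) = 38 to 39 hours. This lies inside the stated 35 to 39. A 3-hour break on each of five days would add 15 hours.

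**The case against.** The strongest reply is that this is one wrong total plus leftover wording. The schedule and every visit procedure give 40 minutes, in both periods. The safety section and the telephone script do not define the regimen, and the visit lengths leave no room for two sessions three hours apart. Nothing suggests that participants or arms would be programmed differently from one another, so the randomised comparison is not biased by the discrepancy. On the period parameters, the two periods already differ in number of sessions (5 against 8) and in elapsed time, so they never isolated frequency.

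Most of this stands, and it limits the point. It does not remove the contradiction, because the 40 minutes and the 1220 seconds sit together in the definition, in two places, and no text reconciles them.

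Three stronger readings are tempting but not supported.
- A reader might infer that each description implies a different exposure. Step 3 shows that twice daily at 1220 s and once daily at 40 minutes give nearly the same weekly total.
- A reader might infer that safety checks cover only 20 minutes of a longer session. Section 8.1 says that checks run throughout the session, and section 2.3.1 describes periodic checks with no time limit. Only the stated length is at odds.
- A reader might infer that the device cannot run for 40 minutes. The 30-minute entry is asterisked, its footnote is not visible, and the same list mentions optional customer-specific programs. It is something to confirm and proves nothing by itself.

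**Conclusion.** The definition of the active session is wrong as written: 40 minutes with the stated ramps is 2420 s (2400 s with the ramps inside), while the stated 1220 s is 20 minutes plus ramps. The discrepancy is 1.98-fold per session. The wording in section 8.1, the Day 5 procedure and the telephone script also fails to match the visit procedures. The arithmetic needs no outside assumption. The statement that the script does not fit assumes that the visit lengths are elapsed times that include any break.

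A change of session length between periods is a literal reading of the Study Agent row only; the visit procedures give 40 minutes in both. The plan should settle this explicitly.

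A reader might also infer a loss of power if the shorter session were delivered. The documents do not support a figure for that. It would need an effect proportional to seconds of stimulation, which no section states. The 1.18-unit effect in section 10.3 is an example not tied to any session length, and the session length in the earlier study behind Table 2 is not given. The planned sample size, alpha and power do not use duration and stay as they are.

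Which figure is correct is for the sponsor to decide; the number of places that agree does not settle it.

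**What to change.** - Reconcile the Protocol Summary (Brief Summary and Study Agent rows), section 4.2, section 7.4.3 (Days 1 to 5), section 8.1 and the telephone script to one session length, one number of sessions per day and a total in seconds that agrees arithmetically. Say whether the ramps are included, and whether the total is per session or per week.
- State whether session length is the same in the first week and in maintenance.
- Correct the telephone script so that sessions per day and visit lengths match the protocol.
- Confirm from the device program which duration is delivered, and that the device setting allows it given the asterisked 30-minute entry in section 6.1.1.

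The cost is protocol and script wording and one check of the device program. No participants, visits or analyses are added.

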## 5 STUDY ENROLLMENT AND WITHDRAWAL

### 5.1 PARTICIPANT INCLUSION CRITERIA

In order to be eligible to participate in this study, a participant must meet all of the following criteria:

- DSM-IV diagnosis of schizophrenia, any subtype, or schizoaffective disorder, with refractory auditory hallucinations. Duration of illness >1 year.
- 18 – 70 years old
- Clinically stable for at least 12 weeks i.e. not requiring hospitalization or a change in level of care.
- On current antipsychotic doses for at least 4 weeks
- Experience at least 3 auditory hallucinations per week
- Stable auditory hallucinations as demonstrated by having less than or equal to 20% change in AHRS scores across a 2 week interval during the screening period
- Capacity to understand all relevant risks and potential benefits of the study and to provide written informed consent, OR has a legal guardian who can provide informed consent on the patient's behalf with the patient providing written assent to participate

